3. LIST OF FINAL REPORT TABLES, LISTINGS AND FIGURES

The following tables specified in the SAP mock table TOC, corresponding to the removed deleted analyses, have been removed.

- 14.2.1.7.1 Cumulative Percentage of Subjects with Anti-Chikungunya Neutralizing Activity At or Above Selected Thresholds by Time Point; Immunogenicity Evaluable Population
- 14.2.1.7.2 Cumulative Percentage of Subjects with Anti-Chikungunya Neutralizing Activity At or Above Selected Thresholds by Time Point; mITT Population
- 14.2.2.4 Percentage of Subjects with Anti-Chikungunya Total Antibody Activity At or Above Selected Thresholds by Time Point; Immunogenicity Evaluable Population
- 14.2.4.4 Percentage of Subjects with Anti-VEEV Total Antibody Activity At or Above Selected Thresholds by Time Point; Immunogenicity Evaluable Population

STATISTICAL ANALYSIS PLAN

ADDENDUM Number # 2

Protocol EBSI-CV-317-002

A Phase 2 Open-Label Study to Assess the Safety and Immunogenicity of an Alum-Adjuvanted Chikungunya Virus-Like Particle Vaccine (PXVX0317) in Prior Recipients of Other Alphavirus Vaccines Versus Alphavirus Naïve Controls

23 Feb 2024

CONFIDENTIAL AND PROPRIETARY INFORMATION

Signature Page

Biostatistician	Dated electronically (Date)	See electronic signature
Author		
Medical Writer	Dated electronically (Date)	See electronic signature
Medical Monitor	Dated electronically (Date)	See electronic signature
Biostatistician Reviewer	Dated electronically (Date)	See electronic signature

[Redacted signatures]

TABLE OF CONTENTS

SIGNATURE PAGE.....	2
TABLE OF CONTENTS.....	3
LIST OF ABBREVIATIONS.....	4
1. BACKGROUND AND RATIONALE	5
2. STATISTICAL CONSIDERATIONS	5
3. LIST OF FINAL REPORT TABLES, LISTINGS AND FIGURES	8

LIST OF ABBREVIATIONS

ADaM	Analysis Data Model
CDISC	Clinical Data Interchange Standards Consortium
CSR	Clinical Study Report
IEP	Immunogenicity Evaluable Population
PRNT	Plaque-reduction Neutralizing Titer
SAP	Statistical Analysis Plan
SDTM	Study Data Tabulation Model
TOC	Table of Contents

1. BACKGROUND AND RATIONALE

This addendum is to document both the addition and updating of the following:

- The study data tabulation model (SDTM) structures for the AE (adverse events) and CE (clinical events; the solicited data from the diaries) domains changed to follow the Office of Vaccines Research and Review (OVRR) guidance to provide consistency across studies
- To add the analyses associated with the following exploratory objective:

Exploratory Objective: Evaluate the ability of anti-CHIKV antibodies to CHIKV VLP vaccine to neutralize diverse (other arthritogenic and encephalitic) alphavirus strains.

The endpoints assessed as part of this statistical analysis plan addendum are associated with the analyses of plaque reduction neutralizing test (PRNT₅₀) titers associated with non-vaccine¹ (heterologous) CHIKV genotype strains measured at three time points (Day 1 (pre-vaccination), Day 22, and Day 182) to explore cross-neutralization activity.

2. STATISTICAL CONSIDERATIONS

Analysis Methods for Exploratory Immunogenicity Endpoints

All exploratory analyses will be performed for the IEP.

Heterologous CHIKV genotypes GMT:

The primary model used for the immunogenicity evaluable population is an analysis of variance (ANOVA), with logarithmically-transformed (log₁₀) titers as the dependent variable and study arm, age, and gender as the predictor variables in the model. The least square means estimated from the ANOVA and their 95% CIs will be back-transformed and reported as the group and overall GMT values. The ANOVA model will be used to determine the significance of the difference between the naïve and prior alphavirus groups.

Percentage of participants with seroconversion to the heterologous CHIKV genotype strains:

¹ CHIKV VLP vaccine is comprised of three recombinant CHIKV structural proteins (capsid, envelope 1 and envelope 2) derived from CHIKV Senegal West African strain 37997.

The percentage of participants with a PRNT₅₀ titer ≥ 20 (the lower limit of quantitation in the PRNT assay) and associated Wilson 95% CIs, will be summarized at Days 1, 22, and 182 for each CHIKV strain. The groups will be compared by pairwise Fisher's exact tests on the percentage with seroconversion.

Raw mean fold rise and geometric mean fold rise as compared to CHIKV strain 181/25:

Of particular interest is the ability of serum anti-CHIKV antibodies collected from individuals immunized with CHIKV VLP vaccine in the clinical study, to neutralize other CHIKV strains that are genotypically diverse from the vaccine strain (CHIKV Senegal strain 37997), as measured by PRNT₅₀ titers.

A validated Human SNA Assay was used to measure anti-CHIKV serum neutralizing antibodies (SNA) in the primary endpoint in this study, and throughout CHIKV VLP vaccine clinical development. The Human SNA Assay uses a modified version of CHIKV strain 181/25 engineered to express a luciferase transgene (*luc*) encoding bioluminescent luciferase enzyme (CHIKV-luc) and is based on the capacity of serum antibodies to neutralize (NT₈₀) the CHIKV-luc reporter virus *in vitro*. To explore the relative ability to neutralize the other CHIKV strains, a comparison back to strain 181/25 was performed.

For the comparison against 181/25, for each participant at each time point, the raw heterologous strain titer will be divided by the 181/25 strain titer to provide a raw fold difference. Descriptive statistics will be provided and statistical significance between the treatment groups will be based on a t-test.

As the titers and fold differences are not necessarily normally distributed, an additional analysis of geometric mean of the fold-increase in titer versus strain 181/25 will be provided. To calculate the geometric mean fold-increase and 95% CI, each strain titer will be log₁₀-transformed and the difference versus 181/25 strain computed (other strain minus 181/25 strain). The mean and 95% CI of the differences in the logs will be calculated and then exponentiated to convert to the non-transformed scale. A t-test will be used to compare the log₁₀-transformed difference in log titers between the prior alpha and naïve alpha subjects.

Changes to the safety dataset structures

The original CDISC datasets were based on a flat structure (each symptom per day per participant was its own record). The FDA OVRR guidance requires that the CE dataset for the data based on the diaries have a summary structure similar to the AE data (start and stop of the event) and that any event that carried past the diary collection be summarized with the diary data rather than as an AE. Per the protocol directions, if an event recorded on the diary continued past day 8, the event was to also be recorded as an AE. These data need to be copied to the CE data to reflect the full extent of the diary symptom duration.

As a result, the datasets that comprise the adverse event CDISC domains (AE and CE), need to be updated to reflect the FDA's guidance.

The changes needed are:

AE data

- STDM - leave the diary records in AE.
- Copy the events that start before Day 8 post injection to FACE (turn into flat structure - one record per event per day)
- Set flag in SUPPAE that this is record that was moved.
- Add same flag to ADaM ADAE dataset to exclude this data from the AE summaries to avoid double counting.

CE data

- Copy flat structure from CE to FACE domain.
- Combine the transferred AE data with the 'new' FACE data (see above) to produce a new summary CE record.
- CEDUR should consist of the dates from the CE and AE records combined (per pre-BLA response from FDA) to provide the full duration across the diary collection and into the AE collection time period.

As a result of these structural changes, the tables based on the solicited and unsolicited adverse events will be rerun.

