9.6 Immunogenicity Analysis

All tests will be carried out at a 2-sided significance level of 0.05 and no adjustment for multiplicity will be applied.

Seroconversion Analysis:

The primary immunogenicity analysis will compare prior alphavirus vaccine recipients to alphavirus-naïve controls on the proportion in each group who seroconvert by anti-CHIKV neutralizing antibody at Day 22. Seroconversion is defined as a 4-fold or greater rise over baseline in anti-CHIKV neutralizing antibodies as assessed by a luciferase-based assay.

Specifically, we will test the hypotheses:

$$H_0: P_1 = P_2 \text{ vs. } H_1: P_1 \neq P_2$$

where P_1 and P_2 denote the proportion of subjects who seroconvert in the prior alphavirus vaccine recipients and the alphavirus-naïve controls, respectively.

The significance of the comparison of the pre-exposure groups will be assessed using a Fisher's exact test. The percentage who seroconvert in each group will be presented along with its 95% CI calculated using the Wilson method. A sensitivity analysis of the comparison will be performed using a logistic regression model that incorporates age, gender, and baseline titer as potential predictive factors. Fisher's test comparing seroconversion rates at other time points may also be performed. Similar analyses of the proportion who seroconvert will be conducted on Days 8, 29, 57 and 182 for anti-CHIKV neutralizing antibody and on Days 22 and 29 for total anti-CHIKV, total anti-VEEV and neutralizing anti-VEEV antibodies (secondary endpoints).

Threshold analyses:

The percentage of subjects achieving specified thresholds (e.g., ≥ 40 , 160, and 640 anti-CHIKV antibody titers), and associated Wilson 95% CIs, will also be calculated for Days 1, 8, 22, 29, 57 and 182 for neutralizing antibody and at Days 1, 22 and 29 for total anti-CHIKV, total anti-VEEV and neutralizing anti-VEEV antibodies (secondary end-points). The groups will be compared by pairwise Fisher's exact tests on the percentage achieving each threshold.

GMT analyses:

For the secondary comparisons based on GMT, the hypotheses tested will be

$$H_0: \mu_1 = \mu_2 \text{ vs. } H_1: \mu_1 \neq \mu_2$$

where μ_1 and μ_2 denote the GMT for the prior alphavirus vaccine recipients and the alphavirus-naïve controls, respectively.

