3.1.5. Immunogenicity Evaluable Population (IEP)

The IEP includes all subjects in the exposed population who:

- Have no important protocol deviation or other reason to be excluded as defined prior to database lock.
- Have not received a prohibited medication.
- Provide evaluable serum sample results for baseline and the primary immunogenicity endpoint within the required time frames:
 - Baseline: Day 1 or within 60 days before study vaccine administration
 - Day 22: Day 19 through Day 25, inclusive

In addition, all subjects in the alphavirus-naïve group are required to be seronegative for both CHIKV and VEEV at baseline, where seronegativity is defined as:

- Anti-CHIKV neutralizing antibody levels below the limit of detection (LOD) of 15, determined by luciferase-based assay (NT80)
- Anti-VEEV neutralizing antibody levels below the LOD of 20, determined by Plaque-Reduction Neutralization Test (PRNT80) assay,

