6.1. Primary Immunogenicity Endpoint

The primary immunogenicity endpoint is the anti-CHIKV seroresponse at Day 22 in prior alpha versus naïve alpha subjects, where seroresponse is defined as a 4-fold rise over baseline in anti-CHIKV neutralizing antibodies as determined by a luciferase-based assay (NT80). Note that seroresponse is referred to as seroconversion in the protocol and in the list of endpoints excerpted from the protocol below.

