3. LIST OF FINAL REPORT TABLES, LISTINGS AND FIGURES

The following new and updated tables specified in the SAP addendum 2 mock table TOC will be:

New tables and listing:

Table/Listing	Title
14.2.6.1	Geometric Mean PRNT Titer Against Heterologous Chikungunya Strains
14.2.6.2	Percentage of Subjects with Seroconversion in Anti-Chikungunya PRNT Titer Against Heterologous Chikungunya Strains by Time Point
14.2.6.3	Raw Mean Fold Increase in PRNT Titer of Heterologous Chikungunya Strains Against 181/25 Homologous Strain by Time Point
14.2.6.4	Geometric Mean Fold Increase in PRNT Titer of Heterologous Chikungunya Strains Against 181/25 Homologous Strain by Time Point
16.2.6.4	Anti-Chikungunya PRNT50 Neutralizing Antibody Titers Against Non-vaccine Strains

Revised tables:

Table	Title
14.3.1	High Level Summary of All Solicited and Unsolicited Events
14.3.1.1	Solicited Events by Highest Reported Severity
14.3.1.2	Solicited Events of at Least Severe (Grade 3) Severity
14.3.1.3	Treatment-related Solicited Events by Highest Reported Severity
14.3.2.1	Day of Onset for Subjects who Reported Solicited Events
14.3.2.2	Day of Onset for Subjects who Reported Treatment-related Solicited Events
14.3.3.1	Number of Days with Symptoms for Subjects who Reported Solicited Events
14.3.3.2	Number of Days with Symptoms for Subjects who Reported Treatment-related Solicited Events
14.3.4	Percentage of Subjects with Solicited Events by Day on Study
14.4.4.1	Unsolicited Adverse Events by Preferred Term in Descending Order of Incidence Through Day 29
14.4.5.1	Unsolicited Adverse Events Through Day 29 by System Organ Class and Preferred Term
14.4.5.2	Solicited and Unsolicited Adverse Events Through Day 29 by System Organ Class and Preferred Term
14.4.5.2.1	Solicited and Unsolicited Adverse Events Through Day 29 by System Organ Class and Preferred Term by Race
14.4.5.2.2	Solicited and Unsolicited Adverse Events Through Day 29 by System Organ Class and Preferred Term by Gender
14.4.6	Unsolicited Adverse Events Through Day 29 by System Organ Class, Preferred Term, and Highest Reported Severity
14.4.8	Treatment-related Unsolicited Adverse Events by Preferred Term in Descending Order of Incidence Through Day 29

14.4.9.1	Treatment-related Unsolicited Adverse Events Through Day 29 by System Organ Class and Preferred Term
14.4.9.2	Treatment-related Solicited and Unsolicited Adverse Events Through Day 29 by System Organ Class and Preferred Term

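### SAP Addendum 2 tests as seroconversion what is only seropositivity (PRNT50 of at least 20, even before vaccination), and none of its analyses measures change from Day 1

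*SAP*

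**What the plan says.** SAP Addendum 2, section 2, has an analysis headed as the percentage of participants with seroconversion to the heterologous CHIKV strains. The variable is a PRNT50 titer of at least 20, with 20 described as "the lower limit of quantitation in the PRNT assay) and associated Wilson 95% CIs, will be summarized at Days 1, 22, and 182". The test follows: "The groups will be compared by pairwise Fisher's exact tests on the percentage with seroconversion". New Table 14.2.6.2 (Addendum 2, section 3) carries the same label: "Percentage of Subjects with Seroconversion in Anti-Chikungunya PRNT Titer Against Heterologous Chikungunya Strains by Time Point". Section 1 of the addendum states that Day 1 is pre-vaccination.

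Elsewhere the term has a different meaning. Protocol 9.6: "Seroconversion is defined as a 4-fold or greater rise over baseline in anti-CHIKV neutralizing antibodies". SAP 6.1, which says that its seroresponse is the protocol's seroconversion: "seroresponse is defined as a 4-fold rise over baseline in anti-CHIKV neutralizing antibodies". Protocol 2.4.3 and SAP 6.2 use the 4-fold rise for total anti-CHIKV and for both anti-VEEV assays as well.

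The other immunogenicity analyses in Addendum 2 are:

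- an ANOVA of log10 titers with "study arm, age, and gender as the predictor variables in the model";
- raw and geometric mean fold measures, in which "the raw heterologous strain titer will be divided by the 181/25 strain titer to provide a raw fold difference", participant by participant at each time point.

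**The concern.** A seroconversion rate tabulated before vaccination cannot describe conversion. At Days 22 and 182 the same rule counts as converted anyone who was already at 20 or more on Day 1, whether or not the titer moved. One study report would then use one word with two meanings.

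The exploratory objective concerns neutralization by antibodies to this vaccine, so activity that was there beforehand has to be separated from activity the vaccine induced. The arms are not protected equally. In the immunogenicity evaluable population, "all subjects in the alphavirus-naïve group are required to be seronegative for both CHIKV and VEEV at baseline" (SAP 3.1.5), but prior recipients have no such requirement. The rule also uses other assays (CHIKV NT80 below 15, VEEV PRNT80 below 20) than the PRNT50 analyzed here. Any baseline PRNT50 positivity would therefore fall mainly on the prior-alphavirus arm, where it could raise the apparent conversion rate and hide a deficit.

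**Working it through.** The plan states no figure for this endpoint, so there is none to reproduce. The check has three parts.

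**1. Does anything in Addendum 2 refer to Day 1 as baseline?**

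| New table | Quantity | Compared with Day 1? |
|---|---|---|
| 14.2.6.1 | Geometric mean titer; model on arm, age, gender | No |
| 14.2.6.2 | PRNT50 at least 20 at Days 1, 22, 182 | No |
| 14.2.6.3 | Raw fold against strain 181/25, same time point | No |
| 14.2.6.4 | Geometric mean fold against 181/25 | No |

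The fold increase in the last two titles is between strains, not over time.

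**2. How do the rules classify the same subject?** The 4-fold rule is max(later, 20) / max(Day 1, 20) ≥ 4. Setting values below the limit to 20 is an assumption: SAP 3.3 substitutes the limit of detection when computing fold increase, but Addendum 2 gives 20 only as the limit of quantitation and states no limit of detection.

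| Day 1 → later | Addendum 2 (≥ 20) | 4-fold rise | Negative to positive |
|---|---|---|---|
| <20 → 40 | yes | no | yes |
| <20 → 79 | yes | no | yes |
| <20 → 80 | yes | yes | yes |
| 20 → 20 | yes | no | no |
| 40 → 40 | yes | no | no |
| 40 → 80 | yes | no | no |
| 40 → 160 | yes | yes | no |

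Under the 4-fold rule a baseline-negative subject needs 4 × 20 = 80, against 20 in the addendum. An unchanged 20 or 40 counts as seroconversion at all three visits under the addendum and meets neither conversion definition.

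**3. How much could it matter?** The inputs are the planned 30 per arm (SAP 1.5) and the two-sided 0.05 level (Protocol 9.6). Baseline PRNT50 positivity is not in the documents, so what follows is illustration.

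- Each prior recipient who is positive on Day 1 and does not rise adds 1/30 = 3.3 points (1/25 = 4.0 points with 25 per arm).
- Suppose all naïve subjects convert and k prior recipients do not. With equal arms of n, the two-sided Fisher p-value is 2 × C(n,k) / C(2n,k).
 - n = 30, k = 6 (24/30 versus 30/30): 2 × 593,775 / 50,063,860 = 0.024.
 - n = 30, k = 5, one of the six now counted as converted (25/30 versus 30/30): 2 × 142,506 / 5,461,512 = 0.052.
 - n = 25: 19/25 versus 25/25 gives 0.022; 20/25 versus 25/25 gives 0.050 (0.0502 before rounding, so above 0.05).
- The Day 1 test itself: with no naïve subject positive, it is significant once 6 or more of 30 prior recipients are at 20 or above. If true prior-arm positivity is 0, 10, 20, 30 or 40%, the probability of a significant Day 1 seroconversion difference is 0, 7, 57, 92 or 99%, before any vaccine effect. A baseline-referenced rate at Day 1 is 0% in both arms by definition.

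**The case against.** The case on the other side has real content.

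- **The definition is in plain view, and other thresholds are allowed.** Protocol 2.4.4 and SAP 6.3 permit exploratory humoral analyses with thresholds other than those specified, and the 4-fold definitions are attached to other assays. This justifies a summary at 20, but not calling it conversion or reporting conversion on Day 1.
- **For a subject below 20 on Day 1, a later 20 is a negative-to-positive change.** This stands. In that sense the variable goes wrong only for subjects already positive on Day 1, although it also departs from the study's 4-fold rule for later titers of 20 to 79.
- **SAP 6.3.1 says exploratory humoral data will be handled like the secondary endpoints, which include 4-fold response and fold increase over baseline.** Addendum 2 neither invokes this nor lists such a table. If the rule applies, it supports a Day 1 reference. The main SAP's model for the evaluable population (6.2.1) also omits baseline titer, but there the fold increase over baseline is analyzed separately.
- **The bias may not exist.** Protocol 2.8.2 excludes natural alphavirus infection (criterion 6) and prior chikungunya vaccine (criterion 13) in both arms, so prior-arm positivity would have to come mainly from cross-neutralization. SAP Addendum 1 reports a 4-fold rise in all subjects by the second time point. Away from the boundary nothing turns on one subject: 28/30 versus 30/30 gives p = 0.49 and 29/30 gives p = 1.00. This limits the likely size. It does not settle PRNT50 against other strains, because the Addendum 1 statement concerns the main neutralizing assay.
- **It is exploratory, and the Day 1 row shows baseline positivity by arm.** Both are true. The tests at Days 22 and 182 still ignore that row.

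**Conclusion.** The concern holds. The endpoint is a threshold at the limit of quantitation, with no reference to baseline. Its label contradicts the study's own definition, and no analysis in Addendum 2 measures change from Day 1. These conclusions follow from the text and need no assumption.

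The numerical effect is unknown. It is zero if no prior recipient is at 20 or more on Day 1, or if all who are also rise. Otherwise it is 3.3 points per such non-rising subject at 30 per arm, always toward a higher rate in the prior arm. The 0.024-to-0.052 example is deliberately placed at the significance limit and shows what is possible, not what is expected. The primary and secondary conclusions are untouched, but the table should be corrected.

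**What to change.** In Addendum 2, section 2, and Table 14.2.6.2:

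1. Rename the at-least-20 summary seropositivity and keep it at Days 1, 22 and 182.
2. Report seroconversion at Days 22 and 182 only, as a 4-fold or greater rise over the Day 1 PRNT50 titer for the same strain, in line with Protocol 9.6 and SAP 6.1.
3. State how values below the limit are handled for this assay. If they are set to 20, say so, and note that a baseline-negative subject then needs at least 80.
4. Base the between-arm Fisher test of seroconversion on this variable and show it beside the seropositivity rows.

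The cost is addendum wording, one table title and one derived variable; Day 1 PRNT50 titers are already planned. There are two downsides. Reported rates may be lower, because titers of 20 to 79 no longer count for baseline-negative subjects. The 4-fold rule also asks more of baseline-positive subjects (40 on Day 1 needs 160), which could understate the prior arm. Keeping the seropositivity rows alongside guards against misreading either measure.

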3. LIST OF FINAL REPORT TABLES, LISTINGS AND FIGURES

The following new and updated tables specified in the SAP addendum 2 mock table TOC will be:

New tables and listing:

Table/Listing	Title
14.2.6.1	Geometric Mean PRNT Titer Against Heterologous Chikungunya Strains
14.2.6.2	Percentage of Subjects with Seroconversion in Anti-Chikungunya PRNT Titer Against Heterologous Chikungunya Strains by Time Point
14.2.6.3	Raw Mean Fold Increase in PRNT Titer of Heterologous Chikungunya Strains Against 181/25 Homologous Strain by Time Point
14.2.6.4	Geometric Mean Fold Increase in PRNT Titer of Heterologous Chikungunya Strains Against 181/25 Homologous Strain by Time Point
16.2.6.4	Anti-Chikungunya PRNT50 Neutralizing Antibody Titers Against Non-vaccine Strains

Revised tables:

Table	Title
14.3.1	High Level Summary of All Solicited and Unsolicited Events
14.3.1.1	Solicited Events by Highest Reported Severity
14.3.1.2	Solicited Events of at Least Severe (Grade 3) Severity
14.3.1.3	Treatment-related Solicited Events by Highest Reported Severity
14.3.2.1	Day of Onset for Subjects who Reported Solicited Events
14.3.2.2	Day of Onset for Subjects who Reported Treatment-related Solicited Events
14.3.3.1	Number of Days with Symptoms for Subjects who Reported Solicited Events
14.3.3.2	Number of Days with Symptoms for Subjects who Reported Treatment-related Solicited Events
14.3.4	Percentage of Subjects with Solicited Events by Day on Study
14.4.4.1	Unsolicited Adverse Events by Preferred Term in Descending Order of Incidence Through Day 29
14.4.5.1	Unsolicited Adverse Events Through Day 29 by System Organ Class and Preferred Term
14.4.5.2	Solicited and Unsolicited Adverse Events Through Day 29 by System Organ Class and Preferred Term
14.4.5.2.1	Solicited and Unsolicited Adverse Events Through Day 29 by System Organ Class and Preferred Term by Race
14.4.5.2.2	Solicited and Unsolicited Adverse Events Through Day 29 by System Organ Class and Preferred Term by Gender
14.4.6	Unsolicited Adverse Events Through Day 29 by System Organ Class, Preferred Term, and Highest Reported Severity
14.4.8	Treatment-related Unsolicited Adverse Events by Preferred Term in Descending Order of Incidence Through Day 29

14.4.9.1	Treatment-related Unsolicited Adverse Events Through Day 29 by System Organ Class and Preferred Term
14.4.9.2	Treatment-related Solicited and Unsolicited Adverse Events Through Day 29 by System Organ Class and Preferred Term
14.4.10	Treatment-related Unsolicited Adverse Events Through Day 29 by System Organ Class, Preferred Term, and Highest Reported Severity
